TITLE: Pilot clinical trial to study facial electrical stimulation to promote recovery in patients with Bell's palsy

DATE: 08/18/2017

NCT#:03836989

Protocol

1. Protocol Title

Pilot study of facial electrical stimulation to promote recovery in patients with facial paralysis from Bell's palsy

2. Objectives

PURPOSE: The primary goal of this pilot study is to collect preliminary data and optimize operations for a full-scale randomized controlled trial of electrical stimulation for the treatment of acute facial paralysis caused by Bells palsy at Oregon Health and Science University (OHSU).

In this study, patients with Bell's palsy and features suggesting they will have a poor recovery will receive either usual standard of care treatment, with medication and physical therapy and two different forms of electrical stimulation. Research subjects can receive either sensory stimulation (higher voltage that they can feel) or subsensory stimulation (minimal voltage that they cannot feel) after training by a physical therapist. We intend to recruit 40 patients for this study and to follow them for 3 months.

SPECIFIC AIMS:

AIM 1- To estimate the impact of 3 months of 15 minutes/day of home facial electrical stimulation on recovery of facial symmetry in patients with Bells palsy and poor prognostic factors for recovery as measured by objective photography.

We hypothesize that patients receiving sensory electrical stimulation will have better symmetry at rest and during facial expressions.

AIM 2- To estimate the impact of 3 months of 15 minutes/day of home facial electrical stimulation on recovery and quality of life in patients with Bells palsy and poor prognostic factors for recovery as measured by patient reported outcomes.

We hypothesize that patients receiving sensory electrical stimulation will have better self reported quality of life.

AIM 3-To estimate adherence and tolerability to a 3-month PT-instructed daily 15 minute home program of facial electrical stimulation in patients with Bells palsy and poor prognostic factors for recovery.

We hypothesize that there will be good adherence and tolerance of facial electrical stimulation when taught by an experienced physical therapist. Patients with facial paralysis are highly motivated to improve their probability of recovery.

PRIMARY ENDPOINTS

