It is important to highlight that most current medical insurance covers electrical stimulation of the face. Electrical stimulation is delivered transcutaneously by placing self-adhesive electrodes on the face. Electrical current is used to produce a visible contraction. The device is easily portable and weighs less than 8 ounces. In general, patients pursue electrical stimulation to the face when recommended by their health care providers or find this resource themselves when frustrated by their poor recovery. The clinical community is divided, with some providers advocating the use of electrical stimulation of the face, while other strongly discourage. Clinicians discouraging electric stimulation site concern for worse outcomes based on their observational experience and one study of the facial nerve of mice (Skouras et al 2009). Evidence for the clinical recommendation of electrical face stimulation is much needed. However, this trial is a low burden intervention consistent with current practice.

4. Study Design

We propose conducting a pilot prospective randomized study for patients with Bell's palsy to receive either standard of care or standard of care plus electrical stimulation to include 30 patients. This would be a feasibility study for a larger study. The trial is described using the PICO Model.

Patients: Acute Bell's palsy with poor prognostic factors

We define acute Bell's and Ramsay Hunt syndrome (described two paragraphs below) as having patients present during their first week of paralysis.

Bell's palsy was defined as idiopathic lower motor neuron facial paralysis with absence of other central nervous system symptoms.

Poor prognostic factors for Bell's palsy defined by meeting any of the following factors:

- Complete paralysis
- Age > 60 years of age
- Ramsay Hunt

Patients with incomplete paralysis experience complete recovery 94% of time, while patients with complete paralysis only experience complete recovery 61% of time (OR 17.4 P<0.05). Complete paralysis affects 15% of patients with Bell's palsy. Patients over the age of 60 only experience complete recovery one-third of the time (Peitersen 2004 and Ikeda et al. 2004).

Exclusion criteria:

- Patients younger than 18 years of age
- Allergy to adhesive
- Non English speakers
- Patient with a deep brain stimulator or a pacemaker

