- Patients who do not complete standard of care therapy with steroid therapy or patients who are determined to have a different etiology to explain their facial paralysis will not exit the intervention. We will continue to monitor and analyze separately in post hoc analysis.

Pregnancy, diabetes, and recurrent attacks of facial paralysis will not be considered exclusion criteria. These variables have been identified by some studies as negative prognostic factors (Peitersen 2004 and Navarrette et al. 2001) but not all studies confirm these factors as affecting prognosis (Fuijiwara et al. 2014). Pregnant women will be included in the analysis as the incidence of Bell's palsy is higher in pregnancy (Peitersen 2004). A separate post hoc analysis will be done analyzing these variables.

Patients will be identified for study eligibility through diagnosis billingcodes used at emergency room or urgent care and primary care doctor appointments at OHSU using EPIC reporting workbench (RWB). During a preliminary search of medical charts for cohort discovery, 350 patients were seen at OHSU for facial paralysis last year. 15% of these patients are expected to meet the criteria for complete facial paralysis (n=53 patients). Additional patients will be eligible based on the age risk factor (age greater than 60 years). We hypothesize we will be able to recruit 15 patients into each treatment arm in less than one year (total study members of 30). Emails and flyers will be used to raise awareness of the study at OHSU, community hospitals, and affiliated clinics. We will track how many patients were contacted for study participation, how many met inclusion criteria and how many chose not to participate and why.

A research assistant will contact the patients for recruitment. The PI will place a referral to physical therapy (under a telephone encounter).

Intervention: Electrical stimulation

Patients will be randomized to either electric stimulation or placebo.

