 - a. Reporting palpebral fissure width and corner of the mouth symmetry at rest
 - b. Reporting brow elevation while raising the eyebrow
 - c. Reporting commissure excursion during smile
- 4) Patient satisfaction and treatment tolerability will be reported at three-month intervals by patients using a Likert scale. Tolerability is rated as: very easily tolerated, easily tolerated, moderately tolerated, hardly tolerated, and not tolerated at all.
- 5) Patient reported treatment adherence through use of a diary and patient self-reporting at the three-month mark.
 - a. Use tracking on the device to collect actual use time with date and time used
 - b. Likert scale to report how frequently did the patient perform the electrical therapy: not at all, a little, rather regularly, very regularly, and as advised
- 6) Time to complete recovery
- 7) A standardized telephone interview will be conducted at six-month follow-up to evaluate any further progress and repeat patient reported questionnaires.

5. Study Population

a. Number of Subjects

Subjects planned to be included: 30 patients total with Bell's palsy (15 patients per treatment arm).

During a preliminary search of medical charts for cohort discovery, 350 patients were seen at OHSU for facial paralysis in 2016. We expect 15% of these patients are expected to meet the criteria for complete paralysis (n=53 patients) and additional patients will meet eligibility due to old age greater than 60 years. We believe we will be able to recruit the target number of 15 patients per group in less than a year.

b. Inclusion and Exclusion Criteria

Screening for eligibility

Patients will be identified for study eligibility through CPT billing diagnosis codes used at emergency room or urgent care and primary care doctor appointments at OHSU using EPIC reporting workbench (RWB). Patients with a diagnosis of Bell's will be reported to the researchers of the study, researchers will use EPIC to identify the contact information of the patient to conduct a telephone interview for screening and to check that patients are over 18 years of age.

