Total participation in the study is 3 months. We will also call you at 6 months for a telephone interview. The 6 month interview form is uploaded in this application as well.

To prevent loss of confidentiality, all of the information and photographs collected will be stored under password protected computer at OHSU and only study personnel will have access to these data. The data will be de-identify as early as possible.

[figure not shown]
If a subject withdraws from electric stimulation intervention, we will continue data collection.

Physical therapy is part of routine Bell's palsy care. Physical therapy would be performed or used even if a subject was not in this study. The costs for these services or items will be billed to your insurance.

Block Randomization for Treatment Assignment

We will use stratified, randomized block design to randomly assign study participants into either treatment or control groups with a 1:1 ratio. Four strata will be utilized based on study participant disease status at enrollment: 1) > 60 years of age with incomplete paralysis, 2) > 60 of age with complete paralysis, 3) complete paralysis (\leq 60 years of age), less than 14 days in duration, and 4) complete paralysis (\leq 60 years of age),P greater than 14 days in duration (*Figure 2*). Study patients providing informed consent, meeting inclusion and exclusion criteria, will be assigned and evaluated in a single-blind fashion (i.e. research staff blinded but the patients and the physical therapist will be unblinded). Due to the relatively small sample size (\sim 20 patients for each treatment) and the number of

strata, we will utilize a minimum block size of 2 within each strata to minimize potential imbalances in treatment assignments. All block assignments will be completed to avoid treatment bias and provide even, but potentially unbalanced, numbers of enrollment subjects per strata.

7. Data and Specimens

a. Handling of Data and Specimens

All data and photos will be stored at OHSU computers under password protection. Only research study members will collect and store information. Only study members will have access to the data for analysis.

b. Sharing of Results with Subjects

Results will not be shared with the subjects

c. Data and Specimen Banking

Data from surveys will be stored using a REDCap database.

8. Data Analysis

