- 6. Patient reported treatment adherence through use of a diary and patient self-reporting at the three-month mark.
 - a. Diary of use which will be handed in monthly
 - b. Patient self-reported adherence using a Likert scale. The scale will have the following options for the patient to rate use: not at all, a little (1-2 week), rather regularly (3-5 week), very regularly (5 week on average), and as advised (daily).

Power calculations

When calculating the number of patients to be included in the pilot study, we wanted to have a realistic sample goal. This study is aimed at evaluating feasibility of recruitment and trial implementation. As mentioned earlier, our preliminary chart reviews show 350 patients were seen at OHSU for facial paralysis during 2014. We expect 15% of these patients are expected to meet the criteria for complete paralysis (n=53 patients) and additional patients will meet eligibility due to old age greater than 60 years. We believe we will be able to recruit the target number of 15 patients per group.

From this pilot trial we hope to gain more information on the effect size. Although adverse effects have not been documented in the prior clinical trials, clinicians in the community are still concerned about negative consequences of electrical stimulation that could have been missed by prior trials. In this trial we are aiming at including 15 patients per group for this pilot study, which would detect an adverse effect in 23% of the population with α for Type I error as 0.05 and power at 0.8.

9. Privacy, Confidentiality, and Data Security

Standard institutional practices will be followed as described in the OHSU Information Security and Research Data Resource Guide (http://ozone.ohsu.edu/cc/sec/isg/res_sec.pdf) to maintain the confidentiality and security of data collected in this study. Study staff will be trained with regard to these procedures. Paper files will be stored in locked filing cabinets in restricted access offices at OHSU. Electronic data is stored on restricted drives on the OHSU network. Electronic data will be stored on encrypted computers. Access to data/specimens is restricted to study personnel. Access to data requires OHSU ID/password authentication. Data from paper forms will be migrated to REDCap Database.

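### The protocol gives two enrolment targets, 40 (about 20 per arm) and 30 (15 per arm), and nothing in it reconciles them

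*Combined protocol and SAP*

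**What the plan says.** Two places point to 40 patients:

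- Section 2 (Objectives, Purpose): "We intend to recruit 40 patients for this study and to follow them for 3 months".
- Section 6 (Block Randomization): an approximate "20 patients for each treatment", given as part of the reason for a minimum block size of 2 within four strata.

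Four places point to 30:

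- Section 4 (Study Design, opening): "standard of care plus electrical stimulation to include 30 patients".
- Section 4 (recruitment text): 15 per arm and 30 in total, expected in under a year.
- Section 5a (Number of Subjects): "Subjects planned to be included: 30 patients total", with 15 per arm, and 15 per group repeated in the next paragraph.
- Section 8 (Power calculations): "We believe we will be able to recruit the target number of 15 patients per group", and then "In this trial we are aiming at including 15 patients per group for this pilot study".

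The last of these leads into the protocol's only power statement: an adverse effect in 23% of the population would be detected with type I error 0.05 and power 0.8. No test, sidedness or comparator rate is given. Section 8 also says that the number was chosen as a realistic goal for a feasibility study. Section 12 plans for 15 stimulation machines.

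**The concern.** This is not one mistyped digit. The figures 40 and about 20 per arm agree with each other across two sections, and 30 and 15 agree across four places. The randomisation text assumes one size, while the recruitment claim and the power statement assume the other.

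Two things that the pilot is meant to deliver depend on the number. One is feasibility: enrolling 30 would meet one target and miss the other by a quarter (10/40). The other is estimation: the aims are to estimate effects, and Section 8 hopes to learn the effect size, so the number per arm fixes how precise those estimates can be.

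**Working it through.** **1. The gap.** 2 × 20 = 40 and 2 × 15 = 30. The difference is 10 patients, or 10/30 = 33% of the smaller target. The document gives no dropout rate, evaluable-patient definition or superseded number that would turn one into the other.

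**2. The plan's own power figure.** Inputs from Section 8: 15 per group, 23%, alpha 0.05, power 0.80. The comparator rate is not stated; I assume 0%, because Section 8 says that earlier trials documented no adverse effects. The test is not stated either, so I tried several, all two-sided.

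*Arcsine approximation.* h = 2·arcsin(√0.23) − 2·arcsin(√0) = 1.000. Power = Φ(h·√(n/2) − 1.96).
- n = 15: Φ(2.740 − 1.960) = Φ(0.780) = 0.782, close to the stated 0.80.
- n = 20: Φ(3.163 − 1.960) = Φ(1.203) = 0.886.

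*Fisher's exact test.* With no events in the comparator arm, p first falls to 0.05 or below at 5 events in the other arm, at both sizes (p = 0.042 at 15 per arm, 0.047 at 20). Power = P(X ≥ 5), X binomial(n, 0.23).
- n = 15: 0.250.
- n = 20: 0.501.

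| Method, 23% v assumed 0% | 15 per arm | 20 per arm |
|---|---|---|
| Arcsine | 78% | 89% |
| Uncorrected chi-square, by enumeration | 47% | 71% |
| Pooled normal formula | 51% | 63% |
| Fisher's exact | 25% | 50% |

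The rate detectable with 80% power against 0% is 24.0% at 15 per arm and 18.4% at 20 by arcsine. By Fisher it is about 41% and 31%.

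So the stated figure can be approximately recovered at 15 per arm with one formula. That same formula gives a different figure at 20.

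**3. Sensitivity to the comparator rate.** With the pooled two-sided formula and a comparator rate of 5% instead of 0%, power to detect 23% is 29% at 15 per arm and 37% at 20. The missing comparator rate therefore matters at least as much as the choice between the two sizes.

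**4. Precision of the primary comparison.** Half-width of the 95% confidence interval for a difference in recovery proportions, equal arms: 1.96·√(2p(1 − p)/n). Section 4 gives 61% complete recovery with complete paralysis and one-third in patients over 60, so I use both.
- p = 0.61, n = 15: 1.96·√(0.4758/15) = 0.349.
- p = 0.61, n = 20: 1.96·√(0.4758/20) = 0.302.
- p = 1/3, n = 15: 1.96·√(0.4444/15) = 0.337.
- p = 1/3, n = 20: 1.96·√(0.4444/20) = 0.292.

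The half-width is 34 to 35 points at 15 per arm and 29 to 30 points at 20.

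**The case against.** The best defence is that this is a feasibility pilot whose size was never derived from power. Section 5a, the section dedicated to the number of subjects, says 30 and agrees with Section 8. The figure in Section 6 is marked as approximate, and the argument for small blocks applies with more force at 15 per arm than at 20. The precision differs by only about 5 points, and both intervals are wide. All of that is fair. It makes 30 the likelier intention and the harm modest. It does not remove the contradiction, because Section 2 still states 40 without qualification.

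Several stronger readings are tempting, but the documents do not support them.

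- A reader might infer that the stated 80% power is reached at neither size. That is so for Fisher, chi-square and the pooled formula against 0%. It is not so in general: arcsine comes within 2 points at 15 per arm and exceeds 80% at 20. With test and comparator unstated, the flat claim cannot be made.
- A reader might infer that a 40-patient trial would be underpowered. For a given test, more patients give more power. The defect is an undefined target, not a larger one.
- A reader might infer that the team could choose between 30 and 40 after seeing results. Section 8 has the primary photographs graded by treatment-blinded raters at the end of the study, Section 4 blinds everyone except patient and therapist, and no interim look is planned. Study personnel do judge recovery during follow-up, but no comparison by arm is scheduled before enrolment ends.
- A reader might divide each target by the 53 patients expected per year and call the recruitment demand excessive. The 53 counts complete paralysis only. Patients over 60 and those with Ramsay Hunt also qualify, and outreach extends beyond the one institution, so the true fraction cannot be computed.
- The 15 machines in Section 12 might seem to settle the target at 15 per arm. They do not, since the text does not say whether devices are reused or whether both arms need one.

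**Conclusion.** The contradiction stands: 40 (about 20 per arm) in Sections 2 and 6, against 30 (15 per arm) in Sections 4, 5a and 8, a gap of 10 patients with no explanation. As a result, success in recruitment is undefined, and the expected half-width for a recovery difference is either about 35 or about 30 points, assuming 61% recovery in both arms.

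The power line belongs to 15 per arm only. Its support at that size depends on an assumed 0% comparator and on the arcsine approximation; under an exact two-sided test the power is far lower at both sizes. What can be said is that the line is incompletely specified, not that it is wrong under every method. Sample size is a basic design figure and the correction is simple, so it should be made even though the trial is a pilot.

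**What to change.** Choose one total and one per-arm number and state them identically in Sections 2, 4, 5a, 6 and 8. If the two figures were meant as enrolled and evaluable patients, say so and give the dropout rate that links them. Check the machine count in Section 12 against the chosen number.

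Restate the power line at that number with its test, sidedness and comparator rate. If an exact two-sided test against 0% is used, the rate detectable with 80% power is about 41% at 15 per arm or 31% at 20. Because the aims are framed as estimation, it would also help to give the expected confidence interval half-width for the recovery difference.

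The cost is protocol wording only. The one real downside is that the advertised detectable rate becomes less favourable than 23% if an exact test is adopted.

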Electrical stimulation of the face could potentially reduce these sequelae. Electrical stimulation is thought to lead to selectivity in the regeneration of motor nerves and decreased muscle atrophy. Selectivity means the nerves regrow and innervate a specific muscle, as opposed to nerves that regrow aberrantly and innervate several muscles making fine control of movement difficult and spasms more likely to occur. By stimulating muscles deprived of electrical nerve input, atrophy is prevented and potentially muscles are more receptive to reinnervation. The theoretical benefits of electrical stimulation have been discussed extensively and replicated in laboratories, but the challenges have been in successfully incorporating electrical stimulation into the clinical setting. As our efforts in the clinic continue, our understanding of electrical stimulation has continued to improve. Successful examples of the use of electrical stimulation in other parts of the body are emerging. Gordon et al. used electrical stimulation acutely after injury to the median nerve for carpal tunnel syndrome patients with substantial axonal loss. Accelerated recovery was seen in this randomized controlled trial (Gordon et al. 2009). Electrical stimulation is also used to accelerate nerve re-growth after facial nerve reparative surgery in animal models when a nerve transection is being treated (Huang et al 2009, Hadlock et al 2010).

Five published clinical trials have examined electrical stimulation of the face during acute Bell's palsy (Tuncay et al. 2015, Alakram et al. 2010, Manikandan et al. 2006, Flores et al. 1998 and Mosforth and Taverner 1958). Two trials reported mild benefit from electrical therapy (Tuncay et al. 2015 and Manikandan et al. 2006), while the rest showed no difference in recovery. Worse recovery with electrical stimulation has not been reported. Given the design of the trials, the effect of electrical stimulation on the face could be underestimated. Patient selection in prior studies is a concern. Often patients with incomplete paralysis are the only patients included in the study, although 94% of patients with incomplete paralysis are expected to recover completely, in contrast to 61% of patients with complete paralysis (Peitersen 2004, Tuncay et al. 2015). Patients with complete paralysis who could

benefit the most are often not included in these studies. The number of patients in the prior trials ranges from 16 to 149, hence the some studies could be underpowered. The length of therapy in some of the studies could be insufficient to see an effect. For example, Alakram et al. only treated patients for 30 minutes weekly for 3 months and Manikandan et al. only treated patients for three times per week, for two total weeks. In severe cases of Bell's palsy, recovery may not begin for many months, making two weeks of electrical therapy potentially insufficient. Outcome assessment could be improved upon by using blinded objective measurements of standardized photographs at rest and with different facial expressions. Having two evaluators allows for better scrutiny of inter-rater reliability. Only one trial (Tuncay et al. 2015) reported treatment-blinded assessment of outcomes. Past trials have greatly relied on estimation of recovery by investigators using the House Brackmann scales. The House Brackmann scale is a well-established scale first described in 1958. It classified patients into 6 categories of global facial function from normal function to complete paralysis. Facial spasms and synkinesis are not considered in the scale. It is difficult to use this scale to describe intermediate levels of recovery, in which some degree of residual weakness exists. Finally, the time of follow up is an important consideration. Spasms and synkinesis tend to develop six months or longer after initial onset of paralysis in severe cases. Length of follow up in prior studies has averaged three months and often is not reported. We would like to perform a trial that addresses these limitations.

It is important to highlight that most current medical insurance covers electrical stimulation of the face. Electrical stimulation is delivered transcutaneously by placing self-adhesive electrodes on the face. Electrical current is used to produce a visible contraction. The device is easily portable and weighs less than 8 ounces. In general, patients pursue electrical stimulation to the face when recommended by their health care providers or find this resource themselves when frustrated by their poor recovery. The clinical community is divided, with some providers advocating the use of electrical stimulation of the face, while other strongly discourage. Clinicians discouraging electric stimulation site concern for worse outcomes based on their observational experience and one study of the facial nerve of mice (Skouras et al 2009). Evidence for the clinical recommendation of electrical face stimulation is much needed. However, this trial is a low burden intervention consistent with current practice.

4. Study Design

We propose conducting a pilot prospective randomized study for patients with Bell's palsy to receive either standard of care or standard of care plus electrical stimulation to include 30 patients. This would be a feasibility study for a larger study. The trial is described using the PICO Model.

Patients: Acute Bell's palsy with poor prognostic factors

We define acute Bell's and Ramsay Hunt syndrome (described two paragraphs below) as having patients present during their first week of paralysis.

Bell's palsy was defined as idiopathic lower motor neuron facial paralysis with absence of other central nervous system symptoms.

Poor prognostic factors for Bell's palsy defined by meeting any of the following factors:

- Complete paralysis
- Age > 60 years of age
- Ramsay Hunt

Patients with incomplete paralysis experience complete recovery 94% of time, while patients with complete paralysis only experience complete recovery 61% of time (OR 17.4 P<0.05). Complete paralysis affects 15% of patients with Bell's palsy. Patients over the age of 60 only experience complete recovery one-third of the time (Peitersen 2004 and Ikeda et al. 2004).

Exclusion criteria:

- Patients younger than 18 years of age
- Allergy to adhesive
- Non English speakers
- Patient with a deep brain stimulator or a pacemaker
- Patients who do not complete standard of care therapy with steroid therapy or patients who are determined to have a different etiology to explain their facial paralysis will not exit the intervention. We will continue to monitor and analyze separately in post hoc analysis.

Pregnancy, diabetes, and recurrent attacks of facial paralysis will not be considered exclusion criteria. These variables have been identified by some studies as negative prognostic factors (Peitersen 2004 and Navarrette et al. 2001) but not all studies confirm these factors as affecting prognosis (Fuijiwara et al. 2014). Pregnant women will be included in the analysis as the incidence of Bell's palsy is higher in pregnancy (Peitersen 2004). A separate post hoc analysis will be done analyzing these variables.

Patients will be identified for study eligibility through diagnosis billingcodes used at emergency room or urgent care and primary care doctor appointments at OHSU using EPIC reporting workbench (RWB). During a preliminary search of medical charts for cohort discovery, 350 patients were seen at OHSU for facial paralysis last year. 15% of these patients are expected to meet the criteria for complete facial paralysis (n=53 patients). Additional patients will be eligible based on the age risk factor (age greater than 60 years). We hypothesize we will be able to recruit 15 patients into each treatment arm in less than one year (total study members of 30). Emails and flyers will be used to raise awareness of the study at OHSU, community hospitals, and affiliated clinics. We will track how many patients were contacted for study participation, how many met inclusion criteria and how many chose not to participate and why.

A research assistant will contact the patients for recruitment. The PI will place a referral to physical therapy (under a telephone encounter).

Intervention: Electrical stimulation

Patients will be randomized to either electric stimulation or placebo.

Plan to use a monophasic waveform having 100microsec pulse rate, at a pulse rate of 35 Hz to voltage that generates twitch contraction or if the research subject can tolerate the voltage needed for a contraction then as high as tolerated. These parameters are taken from clinical trial showing improvement in patients with carpal tunnel (Gordon et al 2009). Electrical stimulation will be produced with the ortho 3 stim which has passes the inspection by the rehabilitation facility for use. The cathode will be placed over the ipsilateral facial muscle to stimulate and the anode behind the ipsilateral ear. All devices are noninvasive without any skin puncture.

Muscles stimulated were:

- 1) Frontalis (FM) to produce brow elevation
- 2) Orbicularis oculi (OOc) to produce eyelid closure
- Zygomaticus major muscle (ZMM) to produce elevation of the oral commissure superiorly and posteriorly
- 4) Orbicularis oris (OOr) to produce lip pursing

Patients are asked to mimic the movements produced by electrical stimulation voluntarily on the nonparalyzed side of the face in front of a mirror during therapy. Electrical stimulation is performed concurrently with facial exercises and mirror therapy. Initially, electrical stimulation is performed with a therapist twice before transitioning to home patient-driven electrical stimulation (duration of first appointment is 40 minutes). Ten contractions of each muscle group will be performed. A hand out will be provided for patients to take home and review the instructions on how to perform home electrical stimulation.

Home electrical stimulation is to be performed for 12 minutes daily (3 mins per muscle). Compliance is defined as performing the electrical stimulation 5 of 7 days of the week.

Duration of therapy: Therapy is to start during the first week of onset of facial paralysis and be used daily for three months or sooner until complete recovery is achieved, as judged by study personnel. The design for electrical stimulation was derived from review of the literature and from focus groups with two physical therapists that treat facial paralysis. OHSU has a physical therapist, [name], who is trained in electrical stimulation of the face and has been providing electrical stimulation for patients being treated at OHSU. [name] will be a collaborator in this trial.

The physical therapist will meet with patients twice. The first session will be 1 hr and will include evaluation and treatment showing patients how to use the electric stimulation machine. The second session will only be 30 min and will be 1 to 2 weeks after the first session. During the second session the participants will demonstrate how they perform electric stimulation.

Comparison: Subsensory electrical stimulation

The electric stimulation device has a placebo setting that delivers minimal electricity.

The settings will be the same as the intervention, the voltage will be below the earliest point at which patients feel the electricity.

The patient and physical therapist will not be blinded. The rest of the research team will be blinded.

All patients will receive steroids (prednisolone 25mg by mouth twice daily, or an equivalent regimen) and Ramsay Hunt syndrome patients should receive antivirals at standard doses (acyclovir 200mg five times a day) (Sullivan et al. 2007).

Outcome:

Primary outcome: Proportion of patients with complete recovery at one, two, and three months Complete recovery is defined as symmetry at rest and symmetry during movement without evidence of synkinesis.

To evaluate for complete recovery, standardized photos of patients at rest, and during movement, will be evaluated by three treatment-blinded otolaryngologists. Recovery will be measured using the eFACES assessment with is a clinician-graded electronic assessment with high inter-rater reliability.

The photos will be standardized as follows:

- Frontal face photo at rest
- 2) Frontal face photo with strong eyelid closure (which shows midface, chin and neck synkinesis)
- Frontal face photo with strong smile (which shows periocular synkinesis and oral commissure movement)

Secondary outcomes:

- 1) House Brackmann scale scoring will be determined by the three otolaryngologists, reported as an average of their three scores after evaluating the three photos mentioned in the primary outcome.
- 2) Patient reported, facial nerve specific, validated quality of life questionnaires:
 - FaCE scale (Khan et al. 2001) measured facial movement, facial comfort, oral function, eye comfort, lacrimal control, and social function.

- b. Synkinesis Assessment Questionnaire (Mehta et al. 2007)
- Objective measurements of facial symmetry at rest and with facial expression as measured by MEEI FACE-gram program.
 - a. Reporting palpebral fissure width and corner of the mouth symmetry at rest
 - b. Reporting brow elevation while raising the eyebrow
 - c. Reporting commissure excursion during smile
- 4) Patient satisfaction and treatment tolerability will be reported at three-month intervals by patients using a Likert scale. Tolerability is rated as: very easily tolerated, easily tolerated, moderately tolerated, hardly tolerated, and not tolerated at all.
- 5) Patient reported treatment adherence through use of a diary and patient self-reporting at the three-month mark.
 - a. Use tracking on the device to collect actual use time with date and time used
 - b. Likert scale to report how frequently did the patient perform the electrical therapy: not at all, a little, rather regularly, very regularly, and as advised
- 6) Time to complete recovery
- 7) A standardized telephone interview will be conducted at six-month follow-up to evaluate any further progress and repeat patient reported questionnaires.

5. Study Population

a. Number of Subjects

Subjects planned to be included: 30 patients total with Bell's palsy (15 patients per treatment arm).

During a preliminary search of medical charts for cohort discovery, 350 patients were seen at OHSU for facial paralysis in 2016. We expect 15% of these patients are expected to meet the criteria for complete paralysis (n=53 patients) and additional patients will meet eligibility due to old age greater than 60 years. We believe we will be able to recruit the target number of 15 patients per group in less than a year.

b. Inclusion and Exclusion Criteria

Screening for eligibility

Patients will be identified for study eligibility through CPT billing diagnosis codes used at emergency room or urgent care and primary care doctor appointments at OHSU using EPIC reporting workbench (RWB). Patients with a diagnosis of Bell's will be reported to the researchers of the study, researchers will use EPIC to identify the contact information of the patient to conduct a telephone interview for screening and to check that patients are over 18 years of age.

A standardized screening telephone interview form is attached. During the interview patients are asked if they are over 60 or if they have complete paralysis. Either of these conditions makes the eligible to participate. If the patients do not have complete paralysis, the telephone interview will ask if they can contact them again in 3 to 5 days to see if the paralysis has worsened and they have developed complete paralysis and are now eligible to participate in the study (Both telephone interviews are included in the same file).

Page 7 of 17

Emails and flyers will be used to raise awareness of the study at OHSU, community hospitals, and affiliated clinics

We will track how many patients were contacted for study participation, how many met inclusion criteria, and how many chose not to participate and why. A screening database Excel file has been included with this application. The database will be kept under password protection at an OHSU computer and will only be accessed by researchers. The database will help prevent patients from being contacted multiple times to participate (EPIC reporting might not be able to differentiate old from new diagnosis). The data will also be evaluated to improve any future trials.

Inclusion and exclusion criteria

We define acute Bell's as having patients present during their first week of paralysis.

Bell's palsy was defined as idiopathic lower motor neuron facial paralysis with absence of other central nervous system symptoms.

Poor prognostic factors for Bell's palsy defined by meeting any of the following factors:

- Complete paralysis
- Age > 60 years of age
- Ramsey Hunt

Exclusion criteria:

- Patients younger than 18 years of age
- Allergy to adhesives
- Non English speakers
- Patients with a deep brain stimulator or a pacemaker
- Patients who do not complete standard of care therapy with steroid therapy or patients who are determined to have a different etiology to explain their facial paralysis will not exit the intervention. We will continue to monitor and analyze separately in post hoc analysis.

